7.2.2 Serious adverse events (SAEs)

A serious adverse event is any untoward medical occurrence or effect that

- results in death;
- is life threatening (at the time of the event);
- requires hospitalisation or prolongation of existing inpatients' hospitalisation;
- results in persistent or significant disability or incapacity;
- is a congenital anomaly or birth defect; or
- any other important medical event that did not result in any of the outcomes listed above due to medical or surgical intervention but could have been based upon appropriate judgement by the investigator.

An elective hospital admission will not be considered as a serious adverse event.

The investigator will report all SAEs, as defined above, to the sponsor without undue delay after obtaining knowledge of the events.

The investigator will report the SAEs, as defined above, through the web portal *ToetsingOnline* to the accredited EC that approved the protocol, within 7 days of first knowledge for SAEs that result in death or are life threatening followed by a period of maximum of 8 days to complete the initial preliminary report. All other SAEs will be reported within a period of maximum 15 days after the sponsor has first knowledge of the serious adverse events.

7.2.3 Suspected unexpected serious adverse reactions (SUSARs)

Not applicable.

7.3 Annual safety report

Not applicable.

7.4 Follow-up of adverse events

All AEs will be followed until they have abated, or until a stable situation has been reached. Depending on the event, follow up may require additional tests or medical procedures as indicated, and/or referral to the general physician or a medical specialist. SAEs need to be reported till end of study within the Netherlands, as defined in the protocol.

7.5 [Data Safety Monitoring Board (DSMB) / Safety Committee]

The additional risk of the use of the BiMobile cup over and above the risks of standard care, as well as the risk of extra X-rays and the placement of tantalum beads, are deemed to be negligible and therefore no DSMB will be established.

8. STATISTICAL ANALYSIS

Descriptive data will be summarized by treatment group. For parameters represented by continuous variables, the summaries will consist of the mean, median, standard deviation, interquartile range, minimum, and maximum values. For categorical variables, the number and percentage in each category will be presented.

Continuous outcome variables and their differences will be analysed with parametrical statistical techniques, unless the normality assumption does not seem reasonable for the data, in which case non-parametric techniques will be considered. A two-sided 0.05 alpha level will be used.

A paired t-test will be used to measure the differences in translations and rotations between RSA and CT.

Actions will be taken to minimize the amount of missing data. If data is missing, this will be handled according to the instructions of the specific measurement instrument, or if not available, imputation techniques will be used to replace the missing data.

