Dual-Mobility (DM) acetabular cups are thought to provide more stability and biomechanically reduce the risk of (early) dislocation compared to regular unipolar acetabular cups.(7-10) Potential disadvantages of DM cups are increased liner wear, psoas impingement and loosening. This might result in more revision surgery at mid- and longer term follow-up for the cemented cups, which has been demonstrated in the Dutch and Australian orthopaedic registries.(11, 12) If the cemented fixation technique improves, this might reduce the number of revisions due to loosening in cemented cups. High quality evidence guiding the best technique for cemented fixation is however lacking. There is evidence that enough bone should be removed, including the removal of the subchondral bone plate; this is known as optimal reaming.(13) The risk of implant loosening might be reduced by increasing the amount of cement used for cup fixation. However, it is currently unknown whether the amount of cement, which depends on the size of the cup, affects stability and survival.(14) To fill this gap in knowledge, this study will compare micro migration of the cup, as an indicator for loosening, in a new dual mobility cup (BiMobile, Waldemar Link GmbH & Co. KG, Hamburg, Germany), using a larger or smaller cup size (and thereby different amounts of cement: approximately 2 millimeter (mm) or 4 mm cement mantle). These results will additionally be compared with the Avantage cup (ZimmerBiomet), which is considered as the standard dual mobility cup in the Netherlands.(15, 16) Migration will be measured with Rontgen Stereophotogrammetry Analysis (RSA), which is currently the gold standard for measuring early migration and predicting long term survival of the implant. A relatively new and less intensive way to measure migration of prostheses is the use of computer tomography (CT) scans, however there is still little scientific evidence on how accurately this can be done.(17-21) This study therefore also measures the accuracy with which migration is measured, between CT scans and RSA.

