2.4 Sample size calculation

Based on current RSA studies and the high degree of sensitivity and accuracy of measurements of migration, relatively small patient groups should show statistical significant outcome.(22) A standardized phantom experiment for the model-based RSA, was performed with an acetabulum cup (Delta-TT cup, LINK) under simulated *in-vivo* conditions (Table 1). In such a phantom experiment, there is no actual movement between the components and the bone, therefore, the observed relative motions represent the

measurement error of these specific components using model-based RSA. These standard deviations are good estimations for the accuracy of the method that can be achieved *invivo*. The relative motions presented in table 1 are smaller than the accepted relative motions presented by Baad-Hansen et al.(23)

Table 1: Relative motions of the Delta-TT cup with respect to the acetabulum bone markers calculated using the elementary geometric shape (EGS) model (n = 10).

	Translations (mm)			Rotations (deg)			
	Trans (x)	Long (y)	Sag (z)	Trans (x)	Long (y)	Sag (z)	
Mean	0.001	0.003	-0.009	-0.069	-0.033	0.033	
St. dev	0.094	0.041	0.074	0.182	0.276	0.396	
Min	-0.145	-0.048	-0.113	-0.410	-0.493	-0.833	
Max	0.170	0.098	0.101	0.137	0.314	0.618	

Sample size calculation based on a t-test was done, assuming normal distribution of migration data and standard deviation of translation of 0.3 mm within the patient collective at two years follow-up.(23) When the sample size in each group is 25, a two group 0.05 t-test will have 90% power to reject the null hypothesis that the two cups are not equivalent (= the difference in means, is 0.3 mm or farther from zero in the same direction) in favour of the alternative hypothesis that the means of the two groups are equivalent, assuming that the expected difference in means is 0 and the common standard deviation is 0.3 mm. This difference of 0.3 mm translation can be considered as a clinically relevant difference.

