6. METHODS

6.1 Study parameters/endpoints

6.1.1 Main study parameter/endpoint

Migration of the acetabular cup at two year postoperative, measured with RSA and CT. RSA X-rays will be collected at discharge, 6 weeks, 6 months, 1 year and 2 years after surgery. Low-dose CT scans of the hip will be collected at discharge and 2 years after surgery.

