6.1.3 Other study parameters (if applicable)

Surgical characteristics such as surgical time, blood loss and implant size will be collected from the surgical report. Prior to surgery demographic data and medical history will be collected. Standard radiographs will be used for analysing the quality of the cement mantle (i.e. cement cracks, cortical hypertrophy), component position, rate of radiolucent lines (>2 mm), loosening and subsidence. In addition, CT scans will be used to assess cement mantle thickness and to compare the accuracy with which migration is measured, between CT scans and RSA.

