8.3 Other study parameters

Other study parameters concern surgical characteristics, demographic data, medical history, standard radiographs (to assess the quality of the cement mantle) and CT scans (to assess the cement mantle thickness and to compare with RSA outcomes). These parameters will be analysed and presented in a descriptive manner.

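### The only inferential method named for CT against RSA is a paired t-test, which addresses mean bias but not the measurement accuracy that the protocol sets out to learn

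*Protocol*

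**What the plan says.** The aim appears in the Summary and in the Introduction and Rationale: "This study therefore also measures the accuracy with which migration is measured, between CT scans and RSA". Section 6.1.3 repeats it as one use of the CT scans: "to compare the accuracy with which migration is measured, between CT scans and RSA". The Introduction treats RSA as the reference, "which is currently the gold standard for measuring early migration and predicting long term survival of the implant".

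Section 8 fixes the method: "A paired t-test will be used to measure the differences in translations and rotations between RSA and CT". The general significance rule in the same section is: "A two-sided 0.05 alpha level will be used".

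Section 8.3 lists the comparison of CT with RSA among the other parameters and says: "These parameters will be analysed and presented in a descriptive manner". Section 8.2 applies repeated measures ANOVA or mixed models to the CT data, without mention of RSA.

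The protocol names no limits of agreement, no concordance measure and no acceptable difference between CT and RSA. It sets no rule for what the t-test result would mean for CT.

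**The concern.** Accuracy against a reference method has two parts: systematic offset and scatter between the two readings in the same patient. A paired t-test addresses only the first. Positive and negative errors cancel in the mean, so the p-value cannot show whether individual readings lie close together.

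The protocol itself treats accuracy as a matter of spread. In section 2.4 it uses the standard deviations of the phantom experiment, not the means, as its estimate of RSA accuracy. The test named in section 8 does not match that idea.

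At stake is what the trial can say about CT. If the p-value is the headline result, a non-significant difference invites the reading that CT agrees with RSA. A small, precisely measured offset could be reported as a significant difference even where individual readings lie close together.

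**Working it through.** **The plan's own figure.** There is none for CT against RSA. The only sample-size statement (section 2.4, "When the sample size in each group is 25") concerns equivalence between two cups and has no bearing here.

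**Inputs from the protocol**
- Pairs: "Low-dose CT scans of the hip will be collected at discharge and 2 years after surgery", so each patient gives one two-year migration pair per axis. Three groups of 25 give 75 pairs. Section 6.5 accepts withdrawals down to 20 per group, which gives 60.
- Two-sided alpha 0.05 (section 8).
- Six axes: three translations and three rotations.

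**Assumed inputs.** The documents give neither the bias nor the SD of CT−RSA differences. Zero bias is therefore shown for SDs from 0.05 to 1.0 mm, and a bias of 0.05 mm for SDs from 0.1 to 0.6 mm.

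**Step 1: zero bias.** The statistic is t = mean difference / (SD/√n). With true bias 0 it follows a central t distribution whatever the SD, so the test is non-significant 95% of the time per axis. The limits of agreement, 0 ± 1.96 × SD, differ greatly:

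| SD of differences (mm) | Non-significant | 95% limits (mm) |
|---|---|---|
| 0.05 | 95% | ±0.10 |
| 0.1 | 95% | ±0.20 |
| 0.3 | 95% | ±0.59 |
| 0.6 | 95% | ±1.18 |
| 1.0 | 95% | ±1.96 |

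An extreme case was simulated: CT readings uncorrelated with RSA, both with the same mean and SD 0.3 mm. The SD of the differences is 0.3 × √2 = 0.42 mm and the limits are about ±0.83 mm. The test was still non-significant in about 95% of simulated trials.

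These are per-axis figures. If the six axes were independent, all six would be non-significant in 0.95^6 = 74% of trials.

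**Step 2: a real bias of 0.05 mm.** The noncentrality is (bias/SD) × √n. With 75 pairs it is 0.05/0.1 × 8.66 = 4.33 for SD 0.1 mm, and 0.05/0.3 × 8.66 = 1.44 for SD 0.3 mm.

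| SD (mm) | 95% limits (mm) | Significant, 75 pairs | Significant, 60 pairs |
|---|---|---|---|
| 0.1 | −0.15 to 0.25 | 99% | 97% |
| 0.3 | −0.54 to 0.64 | 30% | 25% |
| 0.6 | −1.13 to 1.23 | 11% | 10% |

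For the same bias, the less precise method is less often called different.

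**Step 3: the same behaviour in the protocol's Table 1 (n = 10).** Applying t = mean/(SD/√10) to the phantom rotations, the least precise axis (z, mean 0.033, SD 0.396 degree) gives 0.033/0.125 = 0.26. The most precise (x, mean −0.069, SD 0.182 degree) gives |t| = 0.069/0.0576 = 1.20. Both are far below the critical 2.26 on 9 degrees of freedom. These are RSA-only phantom data, so they illustrate the test and say nothing about CT.

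**Step 4: can the planned size support limits of agreement?** The 95% CI half-width of a limit is t × √(1/n + 1.96²/(2(n−1))) × SD.
- n = 75: 1.99 × √(0.0133 + 0.0260) = 0.395 SD (0.389 with 1.96 in place of t).
- n = 60: 2.00 × √(0.0167 + 0.0326) = 0.444 SD.

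So the limits can be estimated usefully from the data already planned.

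**The case against.** The best defence is that the protocol claims little for this test. It says that differences will be measured. It does not say that a non-significant result means agreement, and it does not make replacement of RSA by CT an aim. A reader might infer that the plan would certify a CT method that is useless in individual patients. The documents do not support that: there is no pass/fail rule, and nothing in them shows CT to be imprecise.

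A reader might also infer that worse scatter always makes a non-significant result more likely. At zero bias it makes no difference; the effect arises only when a true bias exists.

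The spread may be reported anyway. Section 8.3 promises a descriptive presentation, and section 8 lists the SD, minimum and maximum among its summaries. Applied to the paired differences, these would show scatter, but the protocol does not say that they will be. A test and a description can coexist, so sections 8 and 8.3 fit loosely rather than contradict each other.

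Mean bias is worth knowing, since the migration analyses compare group means. The CT−RSA comparison sits among the other parameters, is absent from the objectives in section 1, and does not affect the RSA comparison between cups.

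All of this stands and limits the weight of the point. It does not make a test of mean bias an analysis of accuracy.

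**Conclusion.** The point holds in a limited form. The only inferential method fixed for CT against RSA does not answer the stated accuracy question. It is non-significant 95% of the time per axis at zero bias whatever the scatter, and its power to detect a given bias falls as scatter grows: from about 99% to about 30% for 0.05 mm with 75 pairs when the SD goes from 0.1 to 0.3 mm.

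The 95% result is a property of the test. The 99% and 30% rest on an assumed bias and SD. The 0.3 mm SD in section 2.4 describes migration between patients, which is a different quantity.

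The harm depends on how the result is read: the risk is that non-significance is taken as agreement. It is also tempting to judge individual CT error against the 0.3 mm and 0.8 degree of section 2.4. Those figures were set for differences between group means, and only the first is called clinically relevant, so the documents do not support that use.

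This should be corrected, but it does not touch the primary comparison.

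**What to change.** In section 8, make the CT−RSA comparison a Bland-Altman analysis of two-year migration for each axis, reporting:
- the mean difference with 95% CI, which carries the information of the paired t-test;
- the SD of the paired differences;
- the 95% limits of agreement with their CIs.

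State that a non-significant mean difference is not evidence of agreement.

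Before the data are analysed, the sponsor should state and justify an acceptable individual difference for translations and for rotations, and judge the limits against it. The 0.3 mm and 0.8 degree should not be taken over automatically. The justification should allow for the fact that the paired differences also contain RSA's own error.

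In section 8.3, refer to this analysis so that both sections describe the same comparison.

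The cost is a few lines of text, the work of justifying the acceptable difference, and a short extra analysis. No further scans, visits or patients are needed.

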8.1 Primary study parameter(s)

The main study parameter is the early migration (translational and rotational movements) of the BiMobile 2 mm cement acetabular cup and the BiMobile 4 mm cement acetabular

Version number: 3.0, date 20-12-2021 23 of 31

cup after two years. RSA data (discharge, 6 weeks, 6 months, 1 year and 2 years postoperatively) will be analysed using repeated measures ANOVA or mixed models if certain data points are missing. The null hypothesis is that there is no significant difference in mean migration at all time points. The alternative hypothesis is that the mean migration is significantly different at one or more time points.

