For the cup rotations, the highest standard deviation was 0.8 degree within the patient collective at two years follow up.(23) When the sample size in each group is 25, a two group 0.05 t-test will have 90% power to reject the null hypothesis that the two cups are not equivalent (= the difference in means, is 0.8 degree farther from zero in the same direction) in favour of the alternative hypothesis that the means of the two groups are equivalent, assuming that the expected difference in means is 0 and the common standard deviation is 0.8 degree.

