6.3.1 RSA procedure

The RSA set-up consist of two synchronized roentgen tubes positioned approximately 1.5 meter above two roentgen cassettes (35 X 43 cm) at a 20° angle to the vertical. Both roentgen tubes simultaneously expose the roentgen film (Figure 2). A calibration box is used to calibrate the experimental set-up.

The RSA X-ray which is taken one or two days after surgery (before loading) is used as baseline. Since the tantalum beads are fixed in the bone around the implants, the position of the implant relative to the bone can be calculated. Taking these bone markers as reference points, the spatial translations and rotations of the component during follow-up can be calculated.(22, 29) The bone markers need to be well fixated in the bone. Bone markers are defined unstable when they move more than 0.3 mm with respect to the other bone markers. Unstable markers will be excluded from analysis.(30) When there are not enough markers visible in the baseline RSA X-ray and this does not improve by placing the patient in another position, the patient will be excluded from the study (secondary exclusion criterium).

[figure not shown]

Figure 2: A uniplanar RSA arrangement. Two X-ray tubes are focused on the joint under examination. A calibration cage is placed underneath the X-ray table. It holds two X-ray films positioned next to each other.(22)

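### The primary parameter in section 8.1 is several migration outcomes with none marked as decisive, so a difference claim based on any one of them carries a false-positive risk above 5%

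*Protocol*

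**What the plan says.** - Protocol 8.1 defines the primary outcome: "The main study parameter is the early migration (translational and rotational movements) of the BiMobile 2 mm cement acetabular cup", together with the 4 mm BiMobile cup, after two years. The arm contrast is clear. The outcome is plural.
- The hypotheses in 8.1 are of difference: "The null hypothesis is that there is no significant difference in mean migration at all time points", and "The alternative hypothesis is that the mean migration is significantly different at one or more time points". The RSA data "will be analysed using repeated measures ANOVA or mixed models if certain data points are missing".
- Protocol 6.1.1 does not narrow the outcome: "Migration of the acetabular cup at two year postoperative, measured with RSA and CT". No axis or summary measure is named there. Its mention of CT is a separate question about measurement method.
- Protocol 6.3.1 says that with the bone markers as reference, "the spatial translations and rotations of the component during follow-up can be calculated". Table 1 in section 2.4 reports three translations in mm and three rotations in degrees.
- Protocol 8 sets one general level: "A two-sided 0.05 alpha level will be used".
- Protocol 2.4 contains two parallel calculations, each at 0.05 with 25 per group. One is for a translation (SD 0.3 mm, margin 0.3 mm, no axis given). The other is for a rotation: "For the cup rotations, the highest standard deviation was 0.8 degree within the patient collective at two years follow up", with a margin of 0.8 degree. Neither is marked as governing.

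**The concern.** A quantity in millimetres and a quantity in degrees cannot be one variable, so 8.1 as worded describes a family of outcomes. The protocol does not say which member answers the main objective, or how the members combine into one answer.

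Two things follow. First, the components may disagree. One rotation could differ between the 2 mm and 4 mm mantles while every translation does not, and the plan would not say whether mantle thickness then affects migration. The decisive component could be chosen after the results are known. Second, if one significant component is taken as enough, several chances to reject a null of no difference raise the false-positive risk above the stated level. This holds even when only the 2-year value is looked at.

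**Working it through.** **1. The plan's own figure.** Section 2.4 claims 90% power with 25 per group for equivalence, with margin equal to the SD and a true difference of 0. For two one-sided tests, the normal approximation is

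power = 2Φ(δ / (σ√(2/n)) − z) − 1, with δ/σ = 1 and √(25/2) = 3.536.

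- At 0.05 per side: 2Φ(3.536 − 1.645) − 1 = 94.1% (93.4% with the t distribution; 23 per group reach 90%).
- At 0.025 per side: 2Φ(3.536 − 1.960) − 1 = 88.5% (86.7% with t; 27 per group reach 90%).

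The stated 25 lies between 23 and 27, so it reproduces for **one** component. The rotation calculation has the same ratio (0.8/0.8) and gives the same result. Neither makes any allowance for a second component.

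**2. False-positive risk for the difference test of 8.1.**

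Inputs from the protocol: two-sided 0.05 (section 8), a null of no difference (8.1), and either the two quantities sized in 2.4 or the six columns of Table 1.

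Assumptions, not in the protocol: each component is tested at 0.05, any significant component counts as a difference, and the correlations between test statistics are as tabulated.

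Under independence the risk is 1 − 0.95^k:

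- k = 2: 1 − 0.9025 = 9.75%
- k = 3: 1 − 0.8574 = 14.3%
- k = 6: 1 − 0.7351 = 26.5%

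Under equal correlation ρ, the statistics were simulated as Z_j = √ρ·Z_0 + √(1−ρ)·E_j, counting draws with any |Z_j| > 1.96 (at least 200,000 draws per cell):

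| Components | ρ = 0 | ρ = 0.5 | ρ = 0.8 | ρ = 0.9 |
|---|---|---|---|---|
| 2 (one translation, one rotation) | 9.7% | 9.1% | 7.8% | not run |
| 3 | 14.2% | 12.6% | 9.9% | 8.3% |
| 6 | 26.4% | 20.7% | 13.8% | 10.8% |

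Every scenario run exceeds 5%, from 7.8/5 = 1.6 times to 26.5/5 = 5.3 times the stated level.

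**3. Time points.** These figures count one test per component. A single overall test per component across the follow-up visits adds nothing to them. Separate tests at each visit would add more.

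**4. After a change.**

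- One named component at 0.05: risk 5%. Power of a two-sided t-test for a 1-SD difference at 25 per group is 93.4%.
- Six components at the Bonferroni level, 0.05/6 = 0.00833: risk 1 − (1 − 0.00833)^6 = 4.9% under independence. Power for a 1-SD difference on a given component at 25 per group falls to 77.9%. By the normal approximation, 31 per group would restore 90%, against 22 for a single component.

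**The case against.** **The rejection rule is not written down.** A reader might infer that the protocol tests each component at 0.05 and rejects if any one is significant. It says neither. Section 8 gives one level without saying what it applies to, and the phrase about one or more in 8.1 refers to time points, not components. This objection stands, and the figures are therefore conditional on that rule. It does not remove the point, because no other rule is stated and 2.4 uses 0.05 once for translation and again for rotation.

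**Multiplicity handling belongs in the SAP.** An alpha split or testing order may well be in an SAP that is not at hand, and its absence here is no fault. The identity of the primary variable is different. It is protocol content, and 8.1 does not leave it open but fixes it as a multi-component parameter.

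**Six is not the protocol's count of endpoints.** This is right. Table 1 comes from a phantom experiment on another cup, and 8.1 gives no number. A reader might also infer that the risk simply is some figure between 14% and 26%. That would need six components and correlations no higher than about 0.8, and the protocol supplies neither. The two quantities actually sized in 2.4 give about 8 to 10%.

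**The trial is sized for equivalence.** If equivalence were the claim and every component had to lie within its margin, false equivalence would not be inflated. That is correct, but 8.1 states a null of no difference. The mismatch between 2.4 and 8.1 is an issue of its own, and how it is resolved determines which multiplicity rule is needed.

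**Conclusion.** The point holds in conditional form. Section 8.1 fixes the primary parameter as several outcomes under a null of no difference, and neither 8.1, 6.1.1 nor 2.4 says which one decides. If any significant component is read as a difference between the mantle sizes, the false-positive risk is above 5% in every scenario examined. How far above depends on the number of components and their correlation, neither of which the protocol gives. The documents do not support a single unconditional error rate, nor the statement that an any-component rule is prescribed. Nor does the figure apply to an equivalence claim that requires all components to hold.

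This should be corrected. The lack of a defined answer when components disagree remains whatever correlation is assumed.

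**What to change.** In 8.1, name one migration component, or one summary measure, at 2 years as the single primary outcome, tested at two-sided 0.05. Make 6.1.1 and 2.4 match. Fix the choice before any RSA data by arm are seen, which includes the 1-year interim report foreseen in section 6.3 if that report shows results by arm. Report the other components as secondary, with estimates and confidence intervals. This takes a sentence in 8.1 with matching text elsewhere, and no new data or patients. The cost is that the other components lose confirmatory status.

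Alternative: keep several components as primary and test their 2-year differences with Holm's procedure at a family-wise 0.05. The cost is power. At the Bonferroni level for six components, which is Holm's first step, it is about 78% instead of 93% for a 1-SD difference at 25 per group. It would be lower still if groups fall towards the 20 that section 6.5 tolerates. Holm is never less powerful than Bonferroni.

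If the sponsor adopts the equivalence aim of 2.4 in place of the difference null of 8.1, state that all components must lie within their margins. That needs no alpha split, but the chance that all of them succeed together is lower than the 90% computed for one component, unless they are perfectly correlated.

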Dual-Mobility (DM) acetabular cups should provide more stability and biomechanically reduce the risk of (early) dislocation. Potential disadvantages of DM cups are increased liner wear, psoas impingement and loosening. This might result in more revision surgery at mid- and longer-term follow-up for the cemented cups. If the cemented fixation technique improves, this might diminish the disadvantages of more revisions due to loosening in cemented cups. High quality evidence guiding the best technique for cemented fixation is however lacking. The risk of implant loosening might be reduced by increasing the amount of cement used for cup fixation. It is currently unknown whether size of the implant, and thereby the amount of cement, affects stability and survival. To fill this gap in knowledge, this study will compare cup migration, as an indicator for loosening, in a new dual mobility cup (BiMobile, Waldemar Link GmbH & Co. KG, Hamburg, Germany), using a larger or smaller cup size (and thereby different amounts of cement: approximately 2mm or 4mm cement mantle). These results will also be compared with the Avantage cup (ZimmerBiomet), which is yet considered as a standard dual mobility cup in the Netherlands. Migration will be measured with Rontgen Stereophotogrammetry Analysis (RSA), which is currently the gold standard for measuring early migration and predicting long term survival. A relatively new and less intensive way to measure migration of prostheses is the use of computer tomography (CT) scans, however there is still little scientific evidence on how accurately this can be done. This study therefore also measures the accuracy with which migration is measured, between CT scans and RSA. Objective: The main objective of this study is to compare the (early) migration of the cemented BiMobile cup at two year post-surgery between two different cup sizes after standard optimal reaming, and consequently adjusting the cement mantle into circa 2 or 4 mm, in patients with a primary cemented THA. Additionally, the results of the BiMobile cup will be compared to the Avantage cup, which is placed with a standard cup size, resulting in a cement mantle of approximately 2 mm.

Study design: A prospective single centre blinded randomised controlled trial.

Study population: At the outpatient clinic of OLVG, all patients who meet the criteria to undergo a cemented THA will be screened for the in- and exclusion criteria detailed in section 2.

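### The sample size section plans an equivalence test, while the primary analysis tests the opposite null of no difference, so the stated 90% power does not describe the planned test

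*Protocol*

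**What the plan says.** Section 2.4 of the protocol frames the sample size as an equivalence problem. With 25 per group, a two-group t-test at 0.05 is said to have 90% power to "reject the null hypothesis that the two cups are not equivalent" "in favour of the alternative hypothesis that the means of the two groups are equivalent". Non-equivalence is defined for translation as "the difference in means, is 0.3 mm or farther from zero in the same direction", and the planning values are given as "assuming that the expected difference in means is 0 and the common standard deviation is 0.3 mm". The rotation paragraph repeats the argument with a margin and an SD of 0.8 degree: "the difference in means, is 0.8 degree farther from zero in the same direction". The SDs are those at two years.

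Section 8.1 describes the analysis of the same comparison (BiMobile 2 mm against BiMobile 4 mm). It uses repeated measures ANOVA, or a mixed model if data points are missing, over all RSA visits. It states: "The null hypothesis is that there is no significant difference in mean migration at all time points". The alternative is a difference at one or more visits. The opening of section 8 sets a two-sided 0.05 level. Nowhere does section 8 mention 0.3 mm, 0.8 degree, a confidence interval rule or an equivalence test.

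Section 8.2 analyses the BiMobile 2 mm versus Avantage comparison in the same way as the primary parameter. Section 1 (Objectives) says only that migration will be compared. The Summary and Introduction give the motive: "The risk of implant loosening might be reduced by increasing the amount of cement used for cup fixation".

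**The concern.** The two sections state opposite null hypotheses for one comparison. A test of no difference and a test of non-equivalence answer different questions. Failing to reject the first does not establish that the difference is below 0.3 mm, and rejecting it does not establish that the difference is above 0.3 mm.

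Under the planning assumption of a zero true difference, the section 8.1 test is expected to end without significance, and the protocol attaches no conclusion to that outcome. If it were then reported as equivalence, on the strength of section 2.4, the risk of wrongly calling the cups equivalent would be uncontrolled and would rise as the SD rises or the numbers fall. Leaving the choice open until the data are known would allow either conclusion to be claimed.

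This is more than detail deferred to an analysis plan. Section 8.1 fixes a null, an alternative and a model, so an analysis plan that followed one section would contradict the other.

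**Working it through.** **Inputs.** From section 2.4: 25 per group, margin 0.3 mm with SD 0.3 mm, margin 0.8 degree with SD 0.8 degree, expected difference 0, level 0.05, power 90%. From section 8: two-sided 0.05. From section 6.5: withdrawals other than for marker visibility are not replaced while at least 20 per group remain. SDs of 0.4 and 0.5 mm are my assumptions, to show sensitivity. All figures are for a single two-group comparison at 2 years, as in section 2.4. They do not describe the repeated-measures test over all visits in section 8.1.

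**Step 1: the plan's own figure.** Equivalence is tested by two one-sided t-tests (TOST). It is concluded when the CI for the difference lies inside ±0.3 mm. With a true difference of 0, the normal approximation is n per group = 2(SD/margin)²(z₁₋α + z₀.₉₅)², where α is the level per side.

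- α = 0.05 per side (90% CI): 2 × (1.645 + 1.645)² = 21.6, so 22; the exact t calculation gives 23.
- α = 0.025 per side (95% CI): 2 × (1.960 + 1.645)² = 26.0, so 26; the exact t calculation gives 27.

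The stated 25 lies between these. Exact TOST power at 25 per group is 93.4% (90% CI) or 86.7% (95% CI); the normal approximation for the 95% CI gives 88.5%. So the stated 90% is roughly right for an equivalence test, although section 2.4 does not make the level per side clear. Rotation gives the same results because margin/SD is again 1.

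**Step 2: does 90% describe the test in section 8.1?** At the planning value of a zero difference, a two-sided 0.05 test of no difference rejects in 5% of trials and is non-significant in 95%. The 90% is not a property of this test.

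**Step 3: non-significance read as equivalence.** Take a true difference equal to the margin, 0.3 mm. The standard error is SD × √(2/n), the noncentrality is 0.3 divided by the standard error, and the probability comes from the noncentral t with 2n − 2 degrees of freedom.

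| n per group | SD (mm) | Standard error | Noncentrality | P(non-significant) |
|---|---|---|---|---|
| 25 | 0.3 | 0.085 | 3.54 | 6.6% |
| 20 | 0.3 | 0.095 | 3.16 | 13.1% |
| 25 | 0.4 (assumed) | 0.113 | 2.65 | 26.2% |
| 25 | 0.5 (assumed) | 0.141 | 2.12 | 45.3% |

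An equivalence test at 5% per side would pass in at most 5% of trials in every row.

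**Step 4: power under each way of reconciling the sections** (margin/SD = 1).

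| Framework | 25 per group | 20 per group |
|---|---|---|
| Two-sided 5% test, true difference 0.3 mm | 93.4% | 86.9% |
| Equivalence, 90% CI, true difference 0 | 93.4% | 85.6% |
| Equivalence, 95% CI, true difference 0 | 86.7% | 73.8% |

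**The case against.** The best reply is that equivalence appears only in section 2.4 and may be a wording slip. The objective is to compare, the level is two-sided, the rationale hopes that more cement reduces loosening, and section 2.4 itself calls 0.3 mm a clinically relevant difference. Read that way, 25 per group has 93.4% power for the test that section 8.1 describes, taken as a single 2-year comparison. On the protocol's own SD and 25 per group, non-significance at the margin occurs in 6.6% of trials, close to the 5% of a formal equivalence test.

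Much of this stands. It shows that the group size is adequate and that the damage at exactly the planned values is small. It does not remove the contradiction: two explicit and opposite hypotheses remain, and the small excess depends on the SD and numbers holding as planned.

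A reader might infer more than the documents support:

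- **That equivalence is the intended question and section 8.1 is the section in error.** The documents do not settle this.
- **That the trial is too small or cannot be analysed.** Step 4 shows otherwise.
- **That a significant result when the true difference lies inside the margin, say 0.15 mm, is a false conclusion.** It is a correct rejection of no difference; such a difference can be real and still smaller than 0.3 mm.
- **That the cement rationale adds a third framework, superiority.** A two-sided difference test already covers a directional interest.

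**Conclusion.** The point holds as a contradiction between sections 2.4 and 8.1 that should be resolved before results are seen. The 90% power applies to an equivalence test at 2 years, while the stated analysis tests no difference at any visit and uses no margin. A non-significant result under section 8.1 would not show equivalence. Treating it as such when the true difference is 0.3 mm would be wrong in 6.6% of trials on the protocol's figures and 13% at the floor of 20 per group. The range of 26% to 45% holds only if the SD is 0.4 to 0.5 mm, which the protocol does not state. All these rates assume normal data and a single 2-year t-test. Which framework was intended cannot be determined from the protocol, and the group size of 25 is not in question.

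**What to change.** Choose one framework before results are seen and make sections 2.4 and 8.1 agree. State the choice for BiMobile 2 mm versus 4 mm and also for BiMobile 2 mm versus Avantage, since section 8.2 inherits the primary method.

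- **Option (a), difference.** Restate section 2.4 as a two-sided 5% test of a 0.3 mm (0.8 degree) difference at 2 years, with about 93% power at 25 per group for an SD of 0.3 mm (0.8 degree). Keep the test in section 8.1, name the 2-year contrast as primary, and state that non-significance will not be read as equivalence.
- **Option (b), equivalence.** Replace the hypotheses in section 8.1 with a rule that the CI for the 2-year difference must lie within ±0.3 mm (±0.8 degree). Name the axis or axes, among three translations and three rotations, to which the rule applies. State the CI level, reconcile it with the two-sided 0.05 in section 8, and quote the matching power: 93.4% at 25 and 85.6% at 20 per group for a 90% CI, or 86.7% and 73.8% for a 95% CI. These powers are per axis; requiring several axes to pass together lowers them.

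Under either option, report the estimate and its CI against the margin.

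The cost is protocol wording. Patients, visits and measurements do not change. Where the power of the chosen rule falls below 90%, the stated figure has to be corrected.
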